8.1 Standard dose use

The standard dose for the study will be according to the dosing chart listed as Table 4 under 7.1. The maximum total dose will be 4mL per injection visit.

8.2 Dose reductions

Dose reductions with regards to changes in the concentrations of talimogene laherparepvec are not permitted. However, patients may require a reduction in the volume injected due to a disease response (defined in dosing section) or due to local toxicity at the injection site. However, if in the course of administration of talimogene laherparepvec the subject cannot tolerate the full dose due to an injection-related adverse event such as pain, the total volume given should be recorded, and the reason for intolerance should be documented as an adverse event.

8.3 IP treatment delays

If an unexpected DLT occurs, talimogene laherparepvec administration should be delayed until the DLT has resolved to at least CTCAE version 4.0 Grade 1. If talimogene laherparepvec dosing is delayed by more than 6 weeks from the date of the planned dose due to the occurrence of an adverse event that is considered related to talimogene laherparepvec, the subject should be permanently taken off talimogene laherparepvec treatment.

8.4 Adverse Drug Reactions (ADRs)

Important Identified Risks

Important Identified Risks with talimogene laherparepvec treatment are listed below.

Consult the current Investigator's Brochure (IB) for the full information on the Identified

and Potential Risks of talimogene laherparepvec.

- Disseminated herpetic infection including serious cases of disseminated herpetic infection, have been reported in patients treated with talimogene laherparepvec.
- Accidental exposure of healthcare providers (HCP) to talimogene laherparepvec.
- Immune-mediated adverse reactions

Important Potential Risk

Important Potential Risks with talimogene laherparepvec treatment are listed below. Consult the current Investigator's Brochure (IB) for the full information on the Identified and Potential Risks of talimogene laherparepvec.

- Transmission of talimogene laherparepvec from patient to close contacts or HCPs via direct contact with injected lesions or body fluids resulting in symptomatic infection (primary or reactivation).
- Symptomatic herpetic infection due to latency and reactivation of talimogene laherparepvec or wild-type HSV-1 in patients.
- Talimogene laherparepvec-mediated anti-GM-CSF antibody response.

Adverse drug reactions observed in talimogene laherparepvec clinical trials are listed below in Table 6. Consult the current Investigator's Brochure for the full information on ADRs.

	CIOMS Frequency
System Organ Class Preferred Term	(Very Common: ≥10% Common: 1%-<10% Uncommon: <1%)
General disorders and administration site conditions	
Fatigue	Very Common
Chills	Very Common
Pyrexia	Very Common
Influenza like illness	Very Common
Malaise	Common
Axillary pain	Common
Injection site reactions*	Very Common
Gastrointestinal disorders	,
Nausea	Very Common
Vomiting	Very Common
Diarrhea	Very Common
Constipation	Very Common
Abdominal pain	Common
Abdominal discomfort	Common
Musculoskeletal and connective tissue disorders	
Myalgia	Very Common
Arthralgia	Very Common
Pain in extremity	Very Common
Groin pain	Common
Skin and subcutaneous tissue disorders	
Vitiligo	Common
Rash	Common
Dermatitis	Common
Infections and infestations	
Cellulitis	Common
Oral herpes	Common
Incision site infection	Uncommon
Nervous system disorders	
Headache	Very Common
Dizziness	Common
Eye disorders	
Herpetic keratitis	Uncommon

Table 6. ADRs Observed in Talimogene Laherparepvec Clinical Trials

	CIOMS Frequency
System Organ Class Preferred Term	(Very Common: ≥10% Common: 1%-<10% Uncommon: <1%)
Respiratory, thoracic and mediastinal disorders	
Oropharyngeal pain	Common
Obstructive airway disorder	Uncommon
Metabolism and nutrition disorders	
Dehydration	Common
Injury, poisoning and procedural complications	
Contusion	Common
Procedural pain	Common
Wound complication	Common
Wound secretion	Common
Neoplasms benign, malignant and unspecified (incl cysts and polyps)	
Tumour pain	Common
Infected neoplasm	Common
Plasmacytoma at the injection site	Uncommon
Investigations	
Weight decreased	Common
Vascular disorders	
Deep vein thrombosis	Common
Flushing	Common
Blood and lymphatic system disorders	
Anemia	Common
Immune system disorders	
Worsening psoriasis	Uncommon
Pneumonitis	Uncommon
Glomerulonephritis	Uncommon
Vasculitis	Uncommon

* Injection site reactions include: very common term of injection site pain, common terms of injection site erythema, injection site hemorrhage, injection site swelling, injection site reaction, injection site inflammation, secretion discharge, injection site discharge, uncommon term of injection site warmth.

Treatment of ADRs

Subjects will receive medical treatment if injured as a result of study participation. The principal investigator and staff will help the participant get medical care for associated adverse events. The subject or the subject's insurance will be charged for that treatment. The study will not provide monetary compensation for medical treatment. Subjects do not lose legal rights to seek payment by signing the consent form. All reported ADRs will be documented according to safety monitoring and reporting standards (See Section 11 and 12).

8.5 Definition of a Dose Limiting Toxicity (DLT)

Definitions of dose-limiting toxicity:

Toxicity will be evaluated according to CTCAE version 4.0. DLT will be defined as any of the following talimogene laherparepvec-related toxicity during treatment and up to 30 days after end of treatment.

The following herpetic events should be considered as DLTs:

- Serious herpetic events such as herpetic encephalitis, encephalomyelitis or disseminated herpetic infection.
- Any herpetic events (with the exclusion of oral and genital outbreaks) that are at least possibly due to talimogene laherparepvec and require treatment with acyclovir or similar anti-viral agent. Talimogene laherparepvec treatment should be suspended if treatment is required with systemic acyclovir or other anti-virals. If ongoing anti-viral treatment is required, talimogene laherparepvec treatment should be permanently discontinued.

Consider also including the following as DLTs:

- Grade 3 or greater immune-mediated adverse events.
- Any grade plasmacytoma at or near the injection site or evidence of impaired wound healing at the injection site.
- Grade 3 or greater allergic reactions considered at least possibly related to talimogene laherparepvec.
- Grade 4 non-hematologic toxicity.
- Grade 3 non-hematologic toxicity lasting > 3 days despite optimal supportive care;
 - Grade 3 fatigue will not be classified as DLT, irrespective of duration.
- Any Grade 3 or higher non-hematologic laboratory value if:
 - medical intervention is required, or
 - o the abnormality leads to hospitalization, or
 - the abnormality persists for > 1 week unless deemed not clinically important per both investigator and sponsor.
- Grade 3 or 4 febrile neutropenia.

- Grade 4 thrombocytopenia associated with bleeding event requiring intervention.
- Any other intolerable toxicity leading to permanent discontinuation of talimogene laherparepvec.
- Grade 5 toxicity (ie. death).

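### Ten of the twelve dose-limiting toxicity criteria stand under wording that does not clearly adopt them, and the only general rule to delay dosing applies to a DLT that is unexpected, a term left undefined

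*Combined protocol and SAP*

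**What the plan says.** Section 8.5 opens firmly: "DLT will be defined as any of the following talimogene laherparepvec-related toxicity", over a window that runs to 30 days after treatment ends. Two herpetic criteria follow under a heading that tells the reader to treat them as DLTs. The remaining criteria come under a different line, "Consider also including the following as DLTs". They cover immune-mediated, allergic, other non-haematologic, laboratory and haematologic toxicity, injection-site plasmacytoma or impaired wound healing, intolerable toxicity and death. One sub-item in this second list is phrased as a rule: "Grade 3 fatigue will not be classified as DLT, irrespective of duration".

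Section 8.3 gives the dosing consequence: "If an unexpected DLT occurs, talimogene laherparepvec administration should be delayed until the DLT has resolved to at least CTCAE version 4.0 Grade 1". Its second sentence takes a subject off treatment permanently when a delay exceeds 6 weeks "due to the occurrence of an adverse event that is considered related to talimogene laherparepvec".

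Section 8.2 limits the alternatives: "Dose reductions with regards to changes in the concentrations of talimogene laherparepvec are not permitted". A smaller volume is possible for tumour response, "due to local toxicity at the injection site", or when the subject cannot tolerate the injection.

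**The concern.** The trial has no dose escalation, so the DLT definition serves mainly to decide when injections are held. Concentration cannot be reduced, and volume can be reduced only for local reasons or response. A hold is therefore the main stated dosing response to a systemic toxicity, short of stopping.

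Two wordings weaken that response. The first leaves open whether most of the list was adopted. The second attaches the hold to a qualifier without a definition. If either is read narrowly, the required hold may not reach a recognised, drug-related toxicity such as a Grade 3 immune-mediated event. Section 2.2 names two participating sites (Sections 1.1 and 2.1 still say one). Under the same text, one site could hold and the other inject. Up to 4 − 1 = 3 injections remain after Visit 1.

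**Working it through.** No statistical figure in the plan rests on this wording. The check is a count of the criteria and a comparison of every provision that requires or merely permits a hold.

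**Step 1: count the criteria (Section 8.5, top-level bullets).**
- Herpetic: 2.
- Second list: (1) immune-mediated, Grade 3 or worse; (2) plasmacytoma or impaired wound healing; (3) allergic, Grade 3 or worse; (4) Grade 4 non-haematologic; (5) prolonged Grade 3 non-haematologic; (6) non-haematologic laboratory; (7) febrile neutropenia; (8) Grade 4 thrombocytopenia with bleeding; (9) intolerable toxicity causing permanent discontinuation; (10) death. That makes 10.
- Total: 2 + 10 = 12.

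**Step 2: find what else requires a hold or stop.**
- Section 8.5 directs suspension when systemic anti-virals are needed, and permanent discontinuation when that treatment is ongoing. This serves the herpetic criteria.
- Section 11.4 stops the study for a related death or a related herpetic hospitalisation. It stops an individual's treatment when most injected lesions meet withdrawal criteria, when a high-risk feature appears, or when lesion discomfort of Grade 2 or worse persists. The discomfort rule overlaps the second list only for prolonged lesion symptoms. None of the individual criteria names a systemic toxicity.
- Criteria 9 and 10 carry their own consequence.
- Criteria for which 8.3 is the only general hold: 10 − 2 = 8.

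**Step 3: separate text that only permits or detects.** The second sentence of 8.3 presupposes that a delay for a related adverse event can happen, but does not order one. Section 11.5 lists *held* as an action that may be recorded. Section 9.3 has adverse events assessed at each injection visit, and Section 11.2 has the principal investigator review severe events within 24 hours. These steps find events without prescribing a dosing action.

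**Step 4: apply each reading to the 8.**

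| Reading of 8.5 and 8.3 | Toxicities with no required hold |
|---|---|
| List binding, *unexpected* ignored | 0 of 8 |
| List binding, *unexpected* in the reporting sense of Section 12 | possibly 2 of 8 |
| List not binding | 8 of 8 |

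The possible 2 are immune-mediated reactions, an identified risk in Section 8.4, and injection-site plasmacytoma, named in Table 6. In the last row the eight would not be DLTs at all, so they are counted as toxicities without a required hold.

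**Step 5: restart threshold.** Section 8.5 counts "Any grade plasmacytoma at or near the injection site or evidence of impaired wound healing at the injection site" as a DLT, and Section 8.3 lifts the delay at Grade 1. A case first graded 1 would meet the restart condition when found, so the delay would have no effect. This assumes that such a grade exists for these events under CTCAE 4.0 (the tables are not in the documents) and that an event first seen at Grade 1 counts as resolved to Grade 1.

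**Step 6: confirm that the response test is untouched.** For Section 16.2.1, P(success) = Σ over x = 5 to 7 of C(7,x) pˣ(1−p)⁷⁻ˣ · P(Bin(13,p) ≥ 14−x). This gives 0.042 at p = 0.5 and 0.812 at p = 0.8, in line with the stated one-sided 0.05 and 80%. DLTs do not enter the formula.

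**The case against.** The best case against the point is that the text already favours a binding list. The opening sentence of 8.5 covers everything below it. The fatigue exception is written as a rule, and one laboratory condition needs the agreement of investigator and sponsor, which would be odd for criteria never adopted. This stands: a reader might infer that the ten are excluded from the DLT definition, and the documents do not support that. They leave the status open. That the line is leftover template text is itself an inference, though a fair one; Section 11.3 also retains a bracketed prompt to name further forms.

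Second, the reporting sense of *unexpected* is borrowed from Section 12, which governs safety reports to the manufacturer; 8.3 does not refer to it. Whether a Grade 3 immune event is unexpected in that sense depends on the Investigator's Brochure, which is not available here, and Section 8.4 lists the risk without a grade. This also stands, so the middle row is possibly 2 and not at least 2.

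Third, a reader might infer that nothing outside 8.3 compels a hold or stop. That is wrong: the herpetic rule in 8.5 uses the same *should* as 8.3, and 11.4 adds stopping criteria. They cover other events, apart from the partial overlap in Step 2.

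Fourth, oversight is substantial (high-risk rating in Section 11.1, monthly team review in 11.2, monthly board reports in 11.6), and some of these events are rare. Table 6 puts injection-site plasmacytoma below 1%; if that applied here, the chance of any case in 20 subjects would be below 1 − 0.99²⁰ = 0.182, about 18%. This limits how often the wording will matter. It does not tell a site what to do when an event occurs.

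**Conclusion.** The point holds as an ambiguity in a dosing rule. For 8 of the 10 criteria in the second list, the only general provision requiring a hold is 8.3, and its reach depends on two unsettled wordings. The consequence ranges from 0 to 8 of those criteria. The lower end is supported by the opening sentence of 8.5 if the qualifier in 8.3 is given no weight.

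The documents do not support saying that the protocol directs continued dosing after a Grade 3 immune-mediated event. They support only that a hold may not be required, and that two sites could differ while both comply. An investigator remains free to hold.

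The Grade 1 mismatch is real on the text but secondary, and rests on the grading assumptions in Step 5. The matter is one of subject safety and between-site consistency, worth correcting because it alters a stated dosing rule at little cost. The error rates of the two-stage design at its assumed response rates do not change.

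**What to change.** 1. In Section 8.5, replace the line above the second list with *The following are also DLTs:*.
2. In Section 8.3, delete *unexpected*, so that every DLT delays dosing.
3. Optionally, add a lesion-level rule: a lesion with injection-site plasmacytoma is not re-injected; for impaired wound healing, the investigator decides when to resume injecting that lesion, and such a hold does not count toward the subject-level 6-week discontinuation rule.

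The third change should not demand full healing before restart. Section 1.2 admits subjects partly because they heal poorly, target lesions are partially biopsied at screening, and ulceration is among the local effects to be recorded. A full-healing condition could hold lesions often and, without the exemption, push subjects into permanent discontinuation.

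The cost is one heading, one deleted word and, if wanted, the optional rule, with no new procedures. Injections may be held somewhat more often. Fewer injections could in principle affect response, but the documents give no basis for sizing that. Death and toxicity that has already ended treatment need no change.

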9.0 STUDY PROCEDURES

9.1 Screening- Visit 0

Potential subjects will enter the screening period of the study after a completely executed informed consent has been obtained.

- Review of inclusion/exclusion criteria
- Medical and medication history and dermatological history review
- Skin check by the study provider
- Urine pregnancy test (72 hours before enrollment)
- Screening blood work to include a complete blood count (CBC), comprehensive metabolic panel (CMP) and pregnancy test (hCG) if urine pregnancy test comes back positive or inconclusive
- Identification of the target lesions for the study. One subject can have up to 5 TILs. One to three TILs may be on the same anatomical area but will need to be 10 cm apart. Up to 10 TNILs can be followed with no more than 2 TNILs selected in the same anatomical area as a TIL.
- Photographing and measuring of the target lesions
- Biopsy of any suspected non-target skin cancers (ie BCC). If a non-SCC skin cancer is confirmed the corresponding treatment should be completed prior to initiation of study intervention.
- Partial biopsy of lesions suspicious for cSCC (both TILs and TNILs) that have not already been biopsied. A partial shave or small punch biopsy may be done to sample the tissue.
- Vital signs obtained to include blood pressure, pulse, temperature, height and weight
- Ultrasound of TILs at Radiology Department for baseline evaluation (Appendix B)
- Assign screening number starting with the 2-digit site number followed by SCC

and a 3-digit sequential number, starting with -001 and increasing by one for each subject. If a subject fails the screening visit they may be replaced by an additional subject.

9.2 Enrollment- Visit 1

• See 9.3 for enrollment visit details

9.3 On IP treatment

Registered subjects will be treated with talimogene laherparepvec based on lesion size, administered at of 10⁶ (1 million) PFU/mL administered intralesionally for the first visit and 10⁸ (100 million) PFU/mL administered intralesionally for subsequent visits (V2-4). A full description of treatment plan and dosing is outlined in sections 2.4 and 7.1.

Visit 1- First injection visit (7 - 28 days +/- 3 days)

- Skin exam only of target lesions
- Review of all blood work and confirmation to continue in the study
- Review of the biopsies of SCC lesions to confirm SCC diagnosis
- Assess adverse events
- Assess con med changes
- Complete inclusion/exclusion criteria
- Assign subject study number starting with SCC-01 and continue to be assigned sequentially
- Vital signs
- Photograph and measure all target lesions (Appendix A)
- Inject TILs
- Provide patient education on any side effects to expect and the treatment of the injected sites
- Schedule the next injection visit in 3 weeks

Visit 2- Second injection visit (21 days +/- 3 days)

- Vital signs
- Review con meds
- Assess for any adverse events
- Skin exam only of target lesions
- Photograph and measure all target lesions (Appendix A)
- Inject TILs
- Provide patient education on any side effects to expect and the treatment of the injected sites
- Schedule the next injection visit in 2 weeks

Visit 3- Third injection visit (14 +/- 3 days)

- Vital signs
- Review con meds

- Assess for any adverse events
- Skin exam only of target lesions
- Photograph and measure all target lesions (Appendix A)
- Inject TILs
- Provide patient education on any side effects to expect and the treatment of the injected sites
- Complete bloodwork (CBC, CMP)
- Schedule the next injection visit in 2 weeks.

Visit 4- Fourth injection visit (14 +/- 3 days)

- Vital signs
- Review con meds
- Assess for any adverse events
- Skin exam only of target lesions
- Photograph and measure all target lesions (Appendix A)
- Inject TILs
- Provide patient education on any side effects to expect and the treatment of the injected sites
- Schedule the first follow up visit in 4 weeks.

Visit 5- First follow up visit (28 +/- 7 days)

- Vital signs
- Review con meds
- Assess for any adverse events
- Skin exam only of target lesions
- Photograph and measure all target lesions (Appendix A)
- Schedule the second follow up visit in 4 weeks

Visit 6- Second follow up visit (28 +/- 7 days)

- Vital signs
- Review con meds
- Assess for any adverse events
- Skin exam only of target lesions
- Photograph and measure all target lesions (Appendix A)
- Ultrasound of TILs at Radiology Department for follow-up evaluation(Appendix B)
- Schedule the third follow up visit in 6 weeks

Visit 7- Third follow up visit (42 +/- 10 days)

- Vital signs
- Review con meds
- Assess for any adverse events
- Skin exam only of target lesions
- Photograph and measure all target lesions (Appendix A)
- Schedule the next follow up visit in 14 weeks.

Visit 8 - Fourth follow up visit (98 +/- 21 days)

- Vital signs
- Review con meds
- Assess for any adverse events
- Skin exam only of target lesions
- Photograph and measure all target lesions (Appendix A)

Visit 9 – Telephone Follow up (356 +/- 31 days) after Visit 1

- Assess for changes of target lesions
- If active lesion(s) are noted by the participant, they will follow up with a dermatologist and their records will be requested

9.4 Study Assessments

9.4.1 Tumor Measurements:

Tumor measurements will be done at each visit. Imaging assessment with high frequency ultrasound will be done at baseline and at the second follow-up visit (Visit 6). At baseline, up to 5 TILs that are at least 10cm apart will be selected to be followed over the course of the study. Up to 10 TNILs can be followed with no more than 2 TNILs selected in the same anatomical area as a TIL. Responses in TILs and TNILs will be measured serially. Clinical measurements will be performed with a millimeter measuring tape (Appendix A). All measurements will be selected that will be able to be followed clinically and for ultrasound evaluations. The RECIST 1.1 (Appendix B) response criteria will be used to evaluate tumor response. Individual tumor measurements will also be conducted to determine clinical management of TILs and TNILs. The timeframe for the clinical (primary endpoint) and evaluation will be at Visit 6 and for high-frequency ultrasound (secondary endpoints) at Visit 6 as well.

9.4.1.1 Tumor Response

Complete Response (CR): Complete disappearance of all TILs (whether measurable or not, and no new lesions at the site of injection) confirmed by an assessment 8 weeks after the end of the injections (Visit 6).

Partial Response (PR): Decrease in tumor burden $\ge 30\%$ relative to baseline confirmed by an assessment 8 weeks after the end of the injections (Visit 6).

Duration of Overall Response (DOR): DOR is when the time measurement criteria are met for CR or PR (whichever status is recorded first) until the first date that recurrence or progressive disease (PD) is objectively documented, taking as reference for PD the smallest measurements recorded since the treatment started. If no recurrence or PD is documented after PR or CR is observed the time measurement will be performed at Visit 6 for PR and Visit 8 for CR.

Durable Response Rate (DRR): Measured from the time measurement criteria are met for CR or PR (whichever status is recorded first) with the response lasting continuously for > than or equal to 6 months. For PD, the reference will be the
smallest measurements recorded since the treatment started.

Time to progression (TTP): This will be measured from the time treatment is initiated until the first date that recurrence or progressive disease (PD) is objectively documented, taking as reference for PD the smallest measurements recorded since the treatment started.

Progressive Disease (PD): Progression is defined as >20% increase of at least 5 mm in the sum of the longest diameters of the target lesions or increase in tumor burden $\ge 20\%$ relative to nadir (minimum recorded tumor burden) or the appearance of one or more new lesions confirmed by an assessment 8 weeks after the end of the injections (Visit 6).

• **Rapid PD (RPD):** Is defined as an increase of >50% in tumor burden for lesions >2 cm in diameter or 100% tumor burden increase for lesion ≤2cm between visits.

Stable Disease (SD): Not meeting criteria for CR or PR, in absence of PD (Decrease of tumor size <30% to increase in size <20% of less than 5 mm in the sum of the longest diameters of the target lesions).

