9.4.1.2 Clinical Management of TILs and TNILs

Along with assessing the overall tumor response (see Section 9.4.1.1, Tumor Response), each individual lesion will be assessed to determine appropriate clinical management. The RECIST 1.1 (Appendix B) response criteria will also be used to evaluate each individual tumor response.

Individual Lesion Complete Response (IL-CR): Complete disappearance of target lesion (whether measurable or not, and no new lesion(s) at the site of the target lesion) confirmation by an assessment 8 weeks after the end of the injections (Visit 6).

Individual Lesion Partial Response (IL-PR): Decrease in tumor burden $\ge 30\%$ relative to baseline confirmed by an assessment 8 weeks after the end of the injections (Visit 6).

Individual Lesion Progressive Disease (IL-PD): Progression is defined as >20% increase of at least 5 mm in the sum of the longest diameters of the target lesions or increase in tumor burden $\ge 20\%$ relative to nadir (minimum recorded tumor burden) or the appearance of one or more new lesions confirmed by an assessment 8 weeks after the end of the injections (Visit 6).

 Individual Lesion Rapid PD (IL-RPD): Is defined as an increase of >50% in tumor burden for lesions >2 cm in diameter or 100% tumor burden increase for lesion ≤2cm between visits.

Individual Lesion Stable Disease (IL-SD): Not meeting criteria for CR or PR, in

absence of PD (Decrease of tumor size <30% to increase in size <20% of less than 5 mm in the sum of the longest diameters of the target lesions).

	Individual Lesion	Individual	Progressive Disease	Stable Disease
	Complete Response	Lesion Partial	(PD)	(SD)
	(IL-CR)	Response (IL-		
	IL-CR to be	PR)		
	determined at the latest by Visit 6 (8	 IL-PR will be followed and assessed at 	 If IL-PD confirmed in two consecutive visits OR at Visit 6 (8 week 	 IL-SD will be followed and assessed up to
	week follow up), and will be followed for 6	assessed at Visit 6 (8 week follow up)	OR at Visit 6 (8 week follow up), TIL will be withdrawn and	assessed up to Visit 6 (8 week follow up)
	months • No additional	 If IL-SD is documented at 	alternative therapeutic intervention given	 Alternative therapeutic

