16. STATISTICAL CONSIDERATIONS

16.1 Analysis Endpoints

16.1.1 Primary Endpoint

The primary end point is to evaluate the overall response rate (ORR) defined as proportion of subjects who achieved CR and PR in the cSCC TILs. Clinical assessments will be done using a ruler or calipers. Digital photograph of the lesion(s) will be recorded each visit. Through clinical evaluation, CR will be defined as the complete disappearance of all TILs and PR will be defined as at least a 30% decrease in the sum of the diameters of TILs, taking as reference the baseline sum diameters. Progression is defined as >20% increase of at least 5 mm in the sum of the longest diameter recorded or increase in tumor burden \ge 20% relative to nadir (minimum recorded tumor burden) or the appearance of recurrent lesions confirmed by an assessment 8 weeks after the end of the injections (Visit 6). Stable disease (SD) is defined as decrease in tumor size <30% or an increase in size <20%.

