- A sum of the longest diameter (LD) will be calculated and reported as the baseline sum LD for *both TILs and TNILs respectively*. The baseline sum LD will be used as reference by which to characterize the objective tumor.

Response Criteria:

Complete Response (CR):	Disappearance of all TILs
Partial Response (PR):	At least a 30% decrease in the sum of the LD of TILs, taking as reference the baseline sum LD
Progressive Disease (PD):	 >20% increase of at least 5 mm in the sum of the longest diameters of the target lesions Or increase in tumor burden ≥ 20% relative to nadir (minimum recorded tumor burden) Or the appearance of one or more new lesions confirmed by an assessment 8 weeks after the end of the injections (Visit 6).
Stable Disease (SD):	A decrease in tumor size <30% or an increase in size <20% that is less than 5 mm in the sum of LDs of the TILs compared with the smallest sum of the LD recorded.

Evaluation of TILs

Evaluation of TNILs

Complete Response (CR):	Disappearance of all TNILs
Partial Response (PR):	At least a 30% decrease in the sum of the diameters of TNILs, taking as reference the baseline sum LD
Progressive Disease (PD):	 >20% increase of at least 5 mm in the sum of the longest diameters of the target lesions Or increase in tumor burden ≥ 20% relative to nadir (minimum recorded tumor burden) Or the appearance of one or more new lesions confirmed by an assessment at Visit 3.
Stable Disease (SD):	A decrease in tumor size <30% or an increase in size <20% that is less than 5 mm in the sum of LDs of the TNILs compared with the smallest sum of the LD recorded.

Evaluation of best overall response

The best overall response is the best response recorded from the start of the treatment until disease progression/recurrence (taking as reference for PD the smallest measurements recorded since the treatment started). In general, the patient's best response assignment will depend on the achievement of both measurement and confirmation criteria

TILs	TNILs	Recurrent TILs	Overall response
CR	CR	No	CR
CR	Incomplete response/SD/PD	No	CR
PR	Any	No	PR
SD	Any	No	SD
PD	Any	Yes or No	PD

Patients with a global deterioration of health status requiring discontinuation of treatment without objective evidence of disease progression at that time should be classified as having "symptomatic deterioration". Every effort should be made to document the objective progression even after discontinuation of treatment.

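### The 5 mm minimum in the progression definition never operates, because a percentage-only alternative is joined to it by 'or'; small lesion sums are exposed

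*Combined protocol and SAP*

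**What the plan says.** - **Progression, first alternative.** Section 9.4.1.1 asks for a percentage and an absolute rise together, then continues with 'or': "increase of at least 5 mm in the sum of the longest diameters of the target lesions or increase in tumor burden". Section 16.1.1 does the same: "Progression is defined as >20% increase of at least 5 mm in the sum of the longest diameter recorded or increase in tumor burden".
- **Progression, second alternative.** Appendix B sets it out on its own line, for injected and non-injected lesions alike: "Or increase in tumor burden ≥ 20% relative to nadir (minimum recorded tumor burden"). It carries no absolute minimum.
- **Confirmation.** The sentence in 9.4.1.1 goes on: "relative to nadir (minimum recorded tumor burden) or the appearance of one or more new lesions confirmed by an assessment 8 weeks" after the last injection, which is Visit 6. It is unclear whether the confirmation applies to new lesions only or to every alternative.
- **Stable disease.** Appendix B requires "an increase in size <20% that is less than 5 mm in the sum of LDs of the TILs", and 9.4.1.1 is similar. Section 16.1.1 gives the 20% limit without any 5 mm condition.
- **Use.** Duration of response (DOR) and time to progression (TTP) end at the first documented progression or recurrence, judged against the smallest recorded measurement. The durable response rate (DRR) uses the same reference.
- **Measurement.** Section 9.4.1: "Clinical measurements will be performed with a millimeter measuring tape (Appendix A"). Section 16.1.1 and Appendix B name a ruler or calipers. Eligible lesions exceed 0.5 cm and are below 5 cm (6.1), with at most five injected lesions per subject.
- **Lesion management.** Table 7 withdraws an injected lesion "If IL-PD confirmed in two consecutive visits", or on progression at Visit 6.

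**The concern.** A minimum absolute change keeps reading error on small lesions from counting as growth. Here the minimum is written down, but the alternative beside it removes it. Many eligible lesions may be small, and a lesion that shrinks to a small residual has a low nadir. For such sums, one or two millimetres of reading difference would meet the definition.

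Three secondary endpoints depend on it. A false progression shortens DOR and TTP, and it can cost a subject durable-response status. At Visit 6 a second problem appears: one reading can satisfy partial response (against baseline) and progression (against nadir), and the plan does not say which prevails.

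**Working it through.** The plan quotes no error rate for its progression rule, so there is no stated figure to reproduce.

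**1. Is the first alternative redundant?** Let *n* be the nadir sum, *b* the baseline sum (b ≥ n) and *c* the current sum.
- Read against nadir: c > 1.2n implies c ≥ 1.2n.
- Read against baseline: c > 1.2b ≥ 1.2n, so again c ≥ 1.2n.

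Either way the second alternative is already met. Enumerating whole-millimetre sums up to 200 mm found no exception. If burden meant area or volume, a lesion keeping its shape would need a diameter rise of only √1.2 − 1 = 9.5% or 1.2^(1/3) − 1 = 6.3%, so the conclusion would stand.

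**2. What rise triggers progression?** The smallest whole number of millimetres that is at least 0.2 × n:

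| Nadir sum (mm) | Rise that triggers | With a 5 mm minimum |
|---|---|---|
| up to 5 | 1 mm | 5 mm |
| 6 to 10 | 2 mm | 5 mm |
| 11 to 15 | 3 mm | 5 mm |
| 16 to 20 | 4 mm | 5 mm |
| 21 to 25 | 5 mm | 5 mm |

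The minimum stops mattering at 5 / 0.2 = 25 mm, and in whole-millimetre readings already from 21 mm. Eligible lesions start above 5 mm, so the 1 mm row arises only after shrinkage.

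**3. How often would a stable lesion be called progressive?** Simulation of 200,000 single lesions with no true change, read at Visits 1 to 8. Reading error is independent and normal, readings are rounded to 1 mm, and each is compared with the running minimum. The documents give no reading error, so the SD is an assumption, shown as 0.5 / 1.0 / 1.5 mm.

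| True size | At least one false progression, as written | With 5 mm minimum |
|---|---|---|
| 6 mm | 69% / 95% / 99% | 0% / 2% / 27% |
| 10 mm | 38% / 87% / 97% | 0% / 2% / 27% |
| 15 mm | 1% / 47% / 82% | 0% / 2% / 27% |
| 20 mm | 0% / 14% / 54% | 0% / 2% / 27% |
| 25 mm | 0% / 2% / 27% | 0% / 2% / 27% |

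If two consecutive progressive readings are required, the rates at SD 0.5 / 1.0 mm are 60% / 81% (6 mm), 6% / 46% (10 mm) and 0.1% / 12% (15 mm). For three stable 10 mm lesions (sum 30 mm, SD 1.0 mm) the rate is 24% with or without the minimum.

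**4. Can one Visit 6 reading be both?** Baseline 10, nadir 5, Visit 6 = 6 mm: (10 − 6)/10 = 40% below baseline, so partial response; (6 − 5)/5 = 20% above nadir, so progression. For a responder with assumed true sizes 12, 10, 8 and then a steady 6 mm, this overlap occurs at Visit 6 in 25% / 40% of runs at SD 0.5 / 1.0 mm.

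**The case against.** **Was a minimum intended?** A reader might infer from the 5 mm in the stable-disease text that it was. That does not follow. Stable disease in Appendix B needs a rise below 20% and below 5 mm, so its complement is 20% or more, or 5 mm or more. Section 16.1.1 has no 5 mm condition for stable disease at all. Both fit a percentage-only rule. What stands is that the plan states a minimum and then gives it no effect.

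**Is the primary endpoint undermined?** A reader might infer this, but response at Visit 6 is measured against baseline. A falsely progressive stable lesion was a non-responder anyway. Exposure is limited to the overlap in step 4 and to withdrawn lesions.

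**Are the best responders hit hardest?** Not complete responders: their nadir is zero and recurrence governs. The exposed group is partial responders with a small residual, together with subjects who have one or few small lesions.

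**Does confirmation protect?** In part. Before Visit 6, Table 7 needs two consecutive visits, so one stray reading does not remove a lesion. If the Visit 6 clause covers every alternative, the any-visit rates overstate early events. It cannot screen readings at Visits 7 and 8, and Table 7 accepts Visit 6 alone.

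**Are the percentages selective?** They depend on an assumed error, and the highest are for a lesion just above the size limit. The plan gives no size distribution, so no trial-wide rate can be stated.

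**Conclusion.** The wording defeats its own 5 mm minimum in 9.4.1.1, 16.1.1 and Appendix B. This rests on logic alone, given that tumor burden has no separate definition. The practical size depends on lesion sums and reading error: large for single lesions of 6 to 10 mm, moderate at 15 mm, small at 20 mm unless the error SD is 1.5 mm, and nil from 25 mm.

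DOR, DRR and TTP carry most of the effect. They are descriptive Kaplan-Meier summaries in about 20 subjects, with no hypothesis test, and the two-stage decision on response rate is only indirectly touched. This should be fixed before those endpoints are analysed, but it does not invalidate the primary analysis.

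**What to change.** For the endpoint definitions in 9.4.1.1, 16.1.1 and Appendix B:
- Use one criterion: a rise in the sum of longest diameters of at least 20% and at least 5 mm over nadir. Keep recurrence after complete response as a separate criterion.
- Apply the same to the non-injected-lesion definition in 16.1.2 item 8. The text of that item is garbled in the copy reviewed and should be checked.
- Make stable disease the complement: when partial response is not met, a rise of 20% or more but under 5 mm, or of 5 mm or more but under 20%, is stable. Under the present Appendix B wording the second of these is neither stable nor progressive.
- State whether partial response or progression prevails at Visit 6. This is needed even with the new rule: baseline 30, nadir 12, Visit 6 = 18 mm is 40% below baseline and 6 mm (50%) above nadir.

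For the per-lesion progression definition in 9.4.1.2, rapid progression in 9.4.1.1 and 9.4.1.2, and the Table 7 withdrawal triggers, no threshold is proposed. The sponsor must reconcile them with the endpoint definition. For example, a lesion going from 4 to 8 mm doubles, so it would be rapid progression, yet its 4 mm rise would not be progression under the single criterion.

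Cost: a wording amendment, with no new data. The price is lower sensitivity in small lesions. From a 6 mm nadir, progression needs 11 mm (5/6 = 83%), so true regrowth from 6 to 10 mm would not count. Visit 8 comes 14 weeks after Visit 7 and is the last measured visit, so such regrowth may be called late or never, which could lengthen DOR and raise DRR. A sensitivity analysis under the percentage-only rule would show the difference.
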